Time to Event endpoints
Metabolic Management Events

 Time to insulin and time to prandial insulin are defined as follows: For subjects with an event, time to event is the initiation date – treatment start date + 1. For subjects with no event, time to event (censored) is the censor date – treatment start date +1. 
For subjects not receiving any study treatment, who therefore have no treatment start date, time to event will be determined based on date of randomization.
 
The censor date is the latest of clinic visits and phone calls.
 
The definitions of these events are provided in Section 2 of the protocol. Following are more detailed descriptions of event determination:
 
 An insulin event will require more than 3 months use of insulin for subjects in the NI population and will be determined based on data recorded in the Concomitant Medications eCRF form. Specifically this will require use of any type of insulin for a continuous duration of > 3 months (ie > 3*30.4375 days); this could involve multiple medication entries in the eCRF. In the determination of continuous duration of > 3 months, gaps in useage < 7 days will not be considered a break, but gaps in useage \geq 7 days will be considered a break. A prandial insulin event will require more than 3 months use of prandial insulin (i.e., either a prandial-only insulin or a mixed insulin) for subjects in the BI population and will be determined based on data recorded in the Concomitant Medications eCRF form. Specifically this will require use of prandial or mixed insulin for a continuous duration of > 3 months (ie > 3*30.4375 days); this could involve multiple medication entries in the eCRF. In the determination of continuous duration of > 3 months, gaps in useage < 7 days will not be considered a break, but gaps in useage \geq 7 days will be considered a break. Insulin categories are shown in Section 11.13. Initiation date is the date of the earliest medication use after treatment start date. Duration of use = latest stop date of medication – initiation date +1. If a medication stop date is missing, then the date of study completion will be used. 
 Time to first occurrence of a clinically important microvascular event is defined as follows: For subjects with an event, time to event is the first event date – date of randomization +1. For subjects with no event, time to event (censored) is the censor date – date of randomization +1. 
The censor date is the latest of clinic visits and phone calls.
 
The first event date is the date of first occurrence of a clinically important microvascular event. The definition of clinically important microvascular events is provided in Section 6.2.4 of the protocol. Based on this definition, such an event will be determined by one or more of the following items being recorded in the eCRF with a date on or after date of randomization:
 
 Need for renal transplant or dialysis (Renal Impairment eCRF form, Event Treatment/Management: “Treatment required for the renal impairment” = “Renal transplantation”, “Haemodialysis”, or “Peritoneal dialysis”); event date is the corresponding treatment start date. Temporary renal replacement therapy will not

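### SAP section 11.6.4 does not tie the insulin initiation date and duration to the qualifying continuous run, so a true event can be dated from an earlier short course

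*SAP*

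**What the plan says.** Section 11.6.4, under Metabolic Management Events, sets the event rule for time to insulin: "Specifically this will require use of any type of insulin for a continuous duration of > 3 months". Time to prandial insulin has a parallel rule: "Specifically this will require use of prandial or mixed insulin for a continuous duration of > 3 months". Several eCRF entries may be joined to reach that duration. For joining, "gaps in useage < 7 days will not be considered a break", while a gap of 7 days or more is one.

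The same block then gives the derivation: "Initiation date is the date of the earliest medication use after treatment start date. Duration of use = latest stop date of medication", from which the initiation date is subtracted and 1 added. It adds: "If a medication stop date is missing, then the date of study completion will be used". The time to event is the initiation date minus the treatment start date plus 1. Subjects without an event are censored at their last clinic visit or phone call.

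Three other places bear on the point:
- Section 8.1.2 analyses both endpoints by Cox regression with treatment as the only covariate.
- Section 11.11.1 lists both as supportive, with nominal p-values and no multiplicity adjustment.
- Section 2.1, Table 1 records that the 3-month requirement was added to prandial insulin for consistency with the insulin endpoint.

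**The concern.** The event rule works on continuous runs. The derivation works on a span, from the first day of any use to the last day of any use, and that span crosses gaps which the event rule calls breaks. The SAP draws this distinction elsewhere: in section 11.6.2, Extent of Exposure, stop date minus start date plus 1 is the exposure measure that includes breaks, and a separate sum over entries excludes them. Section 11.6.4 uses the first form for an endpoint that needs the second.

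The initiation date feeds directly into the event time, so a wrong date becomes a wrong event time in the Cox model and on the Kaplan-Meier plots. The text also does not say which sentence governs. Two programmers could therefore derive different event dates, and possibly different event sets, from the same medication records. A choice between readings made after unblinding would be post hoc.

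**Working it through.** The SAP gives no event count, power or expected effect for these endpoints, so there is no figure of its own to reproduce.

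**Inputs from the SAP.** One month is 30.4375 days (section 11.6.1), so the threshold is 3 × 30.4375 = 91.3125 days. The 7-day gap rule and the span formula come from section 11.6.4. I count a gap as next start − previous stop − 1, as section 11.1.2 does for days off study treatment. Section 11.6.4 does not state a convention for insulin.

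**Three readings applied to constructed histories.** Days are counted from treatment start as day 1.
- Span: the formula decides both status and date.
- Mixed: the continuity rule decides status, and the earliest use gives the date.
- Run: status, date and duration all come from the first qualifying run.

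| History | Span | Mixed | Run |
|---|---|---|---|
| A: days 60-64 and 300-304 | 304 − 60 + 1 = 245 days; event, day 60 | no event | longest run 5 days; no event |
| B: days 60-64 and 400-600 | 600 − 60 + 1 = 541 days; event, day 60 | event, day 60 | 600 − 400 + 1 = 201 days; event, day 400 |
| C: days 200-400 | 201 days; event, day 200 | event, day 200 | event, day 200 |
| D: days 100-150 and 157-200 (gap 6) | 200 − 100 + 1 = 101 days; event, day 100 | event, day 100 | event, day 100 |
| E: days 100-150 and 158-200 (gap 7) | 101 days; event, day 100 | no event | longest run 51 days; no event |

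C and D agree under all readings. A and E are events only under the span reading. B is dated day 60 under both the span and the mixed reading, 400 − 60 = 340 days before the qualifying run begins.

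**Effect on the hazard ratio, under assumed rates.** None of these inputs is in the SAP: 15,000 subjects per arm, 1.6 years of follow-up, sustained initiation at 0.08 per year on placebo, true hazard ratio 0.5, and 7-day courses that occur independently of sustained initiation. Each row is one simulated data set. The run-based hazard ratio itself varies by chance between rows, so compare within a row.

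| Short courses per year, placebo | Rate ratio for short courses | HR run | HR mixed | HR span | Events, run | Events, span |
|---|---|---|---|---|---|---|
| 0.02 | 0.2 | 0.537 | 0.537 | 0.532 | 2248 | 2264 |
| 0.02 | 0.5 | 0.465 | 0.465 | 0.462 | 2280 | 2295 |
| 0.02 | 1.0 | 0.508 | 0.508 | 0.510 | 2383 | 2404 |
| 0.05 | 0.2 | 0.489 | 0.489 | 0.473 | 2315 | 2369 |
| 0.05 | 0.5 | 0.515 | 0.515 | 0.500 | 2241 | 2316 |
| 0.05 | 1.0 | 0.471 | 0.471 | 0.480 | 2365 | 2447 |
| 0.15 | 0.2 | 0.486 | 0.485 | 0.412 | 2317 | 2619 |
| 0.15 | 0.5 | 0.525 | 0.524 | 0.482 | 2312 | 2696 |
| 0.15 | 1.0 | 0.484 | 0.484 | 0.563 | 2332 | 2893 |

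The span reading moves the hazard ratio toward 1 when treatment does not affect short courses, and away from 1 when treatment reduces them. The shift is at most 0.005 at 0.02 per year, 0.009 to 0.016 at 0.05, and 0.043 to 0.079 at 0.15. Under the mixed reading the shift is at most 0.001 here. That small figure rests on the independence assumption: if subjects who have short courses are also those who later start sustained insulin, case B would be more common.

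**The case against.** The strongest reply is that the event rule is stated separately and explicitly for each endpoint, and that the initiation and duration lines are only derivation detail beneath it. On that reading A and E fail the continuity requirement and are not events. Letting the formula override the rule would leave the 7-day gap rule with no purpose. This largely stands: a reader might infer that the SAP necessarily counts separated short courses as events, but its text does not establish that. It is a risk of the wording. The reply does not help with case B, because "Initiation date is the date of the earliest medication use after treatment start date" still points to day 60.

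A reader might also infer that the treatment effect is diluted. That requires short courses to be unrelated to treatment, on which the SAP says nothing, and the calculations above moved either way.

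A third tempting inference is that the rule "The censor date is the latest of clinic visits and phone calls" is itself at fault, because insulin begun in the last 91 days and still ongoing cannot reach the threshold. The endpoint is defined as insulin of more than 3 months, so such a start does not meet it. In 150 simulated trials (3,800 subjects, 0.8 to 2.6 years of follow-up, 6 initiations per 100 person-years on placebo, true hazard ratio 0.60, no short courses), the requirement reduced events from 299 to 257, about 14%. The hazard ratio was 0.600 when all starts counted, and 0.602 whether censoring was at last contact or 91 days before it. Earlier censoring recovered no events and would give non-positive times to subjects followed for less than 91 days.

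Finally, Listings 36 and 37 show the derived times and Listing 11 the underlying medication, so misdating could be detected. That allows checking afterwards but does not settle the rule beforehand.

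**Conclusion.** The derivation is wrong as written. Initiation date and duration are not tied to the qualifying run and conflict with the break rule in the same section. The early dating of a true event that follows a separate short course holds on any literal reading. The counting of separated short courses as events is conditional on the duration formula being taken to govern.

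The error for one subject can be large (340 days in case B). How many subjects are affected, and which way the hazard ratio would move, cannot be derived from the SAP; the simulated shifts illustrate assumed rates and are not estimates for this trial. The scope is limited to two secondary endpoints with nominal p-values, and the primary MACE analysis is untouched. This is a correction to make before unblinding, not a threat to the trial's main conclusion.

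**What to change.** In section 11.6.4, replace the earliest-use and latest-stop formula, for insulin and for prandial insulin alike, with a run-based definition:
- Join entries for the relevant insulin type when the gap between them is under 7 days, and state how a gap is counted.
- Take the first such run after treatment start that itself lasts more than 3 × 30.4375 days. Its first day is the initiation date.
- Compute duration as the last day minus the first day of that run, plus 1.
- If no run qualifies, there is no event.

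Leave the censoring date and the rule for missing stop dates as they are. The cost is a few lines of SAP text and a small program edit. No new data are needed, and subjects with a single uninterrupted course keep the same result.

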11.6.5. Value Evidence and Outcomes (VEO)

Questionnaires	

 TRIM-D scoring will be done as specified in the TRIM-D Information Booklet [MAPI, 2013] with the exception that missing individual question responses will not be imputed. EQ-5D scoring will be done as specified in the EQ-5D-5L User Guide [Oemar, 2013]. 	

11.7. Appendix 7: Premature Withdrawals & Handling of Missing Data

11.7.1. Premature Withdrawals

Element	Reporting Detail
General	
 Subject study completion (i.e. as specified in the protocol) was defined as completion of all periods of the study up to and including any follow-up period. Follow-up period here refers to continuing follow-up for CV events (i.e. not the 5 week follow-up visit post IP discontinuation). Withdrawn subjects will not be replaced in the study. All available data from subjects who were withdrawn from the study will be listed and all available planned data will be included in summary tables and figures, unless otherwise specified. Per protocol, subjects may prematurely discontinue study drug but are encouraged to remain in the study.

11.7.2. Handling of Missing Data

Element	Reporting Detail
General	
 Missing data occurs when any requested data is not provided, leading to blank fields on the collection instrument : 
 These data will be indicated by the use of a “blank” in subject listing displays unless all data for a specific visit are missing in which case the data is excluded from the table. Answers such as “Not applicable” and “Not evaluable” are not considered to be missing data and will be displayed as such.
Adverse Events	
 Events with missing maximum intensity are considered “Severe” for summaries.
Outliers	
 Any subjects excluded from the summaries and/or statistical analyses will be documented along with the reason for exclusion in the clinical study report.

11.7.2.1. Handling of Missing Dates

Element	Reporting Detail
General	Partial dates will be displayed as captured in subject listing displays.

11.7.2.2. Handling of Partial Dates

Element	Reporting Detail
Death	
 The following rules for missing or partial death dates will be implemented as long as the imputed date is on or after the randomization date. If the imputed date is prior to the randomization date, then the date of randomization will be imputed for the death date.

Element	Reporting Detail
	
 ○ The latest non-missing date of clinic visit or telephone or other contact with subject, endpoint date, AE or SAE date or date last known to be alive based on third party follow-up will be determined. If the year, month, and day of month of the death are missing then the death date will be imputed as the latest of the dates. ○ If only the day of the month of death is missing, then it will be imputed as the first day of the month (e.g., --FEB2016 would impute as 01FEB2016). However, if this imputed date results in a date that is prior to the latest non-missing date of clinic visit or telephone or other contact with subject, endpoint date, AE or SAE date or date last known to be alive based on third party follow-up then impute the missing day of death as equal to this date instead. 
For example:
 
 ▪ If --FEB2016 is given as the death date and there is a non-fatal MI on 08FEB2016, then the imputed date of death would be 08FEB2016 rather than 01FEB2016 such that the death is not before the non-fatal MI. ▪ If --MAR2016 is given as the death date and the latest date is a non-fatal MI on 08FEB2016 then the imputed date of death would be 01MAR2016. ○ If the month and day of the month of death are missing, then they will be imputed as 01JAN (e.g., ----2016 would impute as 01JAN2016). However, if this imputed date results in a date that is prior to the latest non-missing date of clinic visit or telephone or other contact with subject, endpoint date, AE or SAE date or date last known to be alive based on third party follow-up then impute the missing month and day of death as equal to this date instead. 
For example:
 
 ▪ If ----2016 is given as the death date and the latest date is a non-fatal MI on 08FEB2016 then the imputed date of death would be 08FEB2016 rather than 01JAN2016 such that the death is not before the non-fatal MI. ▪ If ----2017 is given as the death date and the latest date is a non-fatal MI on 08FEB2016 then the imputed date of death would be 01JAN2017. 
For deaths that occur after subjects have prematurely withdrawn from the study, missing or partial dates will be imputed as specified above except if the imputation places the death prior to or on the premature withdrawal date. In this case the death date will be imputed as the premature withdrawal date + 1 day.
 
If the date of death provided by the Investigator is missing or partial, then it will be imputed by the date of death as determined by the CEC.

CV events	
 • If event dates are missing or partial and there is not sufficient information to classify the time period of the event, the event will be classified as occurring

Element	Reporting Detail
	
On-treatment and post-randomization. The event will also be considered to have occurred during the follow-up for cardiovascular events as defined in Section 11.6.4.
 
 The following rules for missing or partial event dates for events other than death will be implemented as long as the imputed date is on or after the randomization date. If the imputed date is prior to the randomization date, then the date of randomization will be imputed for the event date. 
 If only the day of the month is missing, impute the first day of the month (e.g., --FEB2016 would impute as 01FEB2016) If the month and day of the month are missing, impute 01JAN (e.g., ----2016 would impute as 01JAN2016) If the year, month, and day of month are missing, impute the randomization date 
If the CV event date provided by the Investigator is missing or partial, then it will be imputed by the corresponding date as determined by the CEC.

Microvascular Events	
 Missing or partial event dates will be handled in a manner similar to that specified for CV Events.
Adverse Events	
 Partial start dates will be imputed as the earliest possible date consistent with the partial date and assigned treatment state. Partial stop dates will be imputed as the latest possible date consistent with the partial date and assigned treatment state.
Medications	
 Partial start dates of medications will be imputed as the earliest possible date consistent with the partial date. In the case of a completely missing start date, the start date will be assumed to be prior to date of the first administration of study drug. Partial stop dates of medications will be imputed as the latest possible date consistent with the partial date. In the case of completely missing stop date, the medication will be assumed to be ongoing.

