4. ANALYSIS POPULATIONS

Population or Analysis	Definition / Criteria	Analyses Evaluated
Intent-To-Treat (ITT) Population	
 • Comprised of all randomized subjects excluding subjects who did not provide consent. • This population will be based on the treatment to which the subject was randomized. • Any subject who is assigned a treatment randomization number by the PPD IRT system 	
 • Primary Endpoint and other Efficacy • Health Outcomes • Study Population (selected outputs)

Population or Analysis	Definition / Criteria	Analyses Evaluated
	will be considered to have been randomized. If there is documented evidence that a subject was randomized in error (not intended by Investigator), inclusion of the subject in the ITT population will be determined prior to unblinding.	
Safety Population	
 Comprised of all randomized subjects who receive at least one dose of study treatment. Subjects who did not provide consent will be excluded. This population will be based on the treatment the subject actually received. If a placebo subject is dispensed and may have used incorrect container(s) and wrong treatment at more than one visit then the subject will be assigned to albiglutide. 	
 Safety Study Population (selected outputs)
Per-Protocol (PP) Analysis	
 Analysis includes all randomized subjects who provide consent and receive at least one dose of study treatment, excludes data prior to treatment start date and data after the date of last dose of study treatment + 56 days, and excludes data via censoring for subjects experiencing specified conditions. Specified conditions that would result in exclusion (via censoring in the analysis) of subject data from the PP analysis are defined in Section 4.1 and Section 11.1. The analysis will be based on the treatment to which the subject was randomized. Data for subjects assigned incorrect study drug will be censored as specified in Section 11.1. 	
 Primary Endpoint assessed using the Per-Protocol analysis
Non-insulin (NI) Population [1]	
 Comprised of subjects in the 'Intent-To-Treat' population who are not on insulin at baseline. Subjects will be included in the NI population based on medication data recorded in the eCRF. 	
 Time to Insulin endpoint

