11.5.2. Baseline and Screening Definition & Derivations

11.5.2.1. Baseline Definitions

The baseline value for an assessment is defined as the last non-missing value assessed on or before treatment start date. Generally the time of assessment is not collected; hence this definition assumes that assessments collected on the same day as treatment start were done prior to treatment start. For creatinine, eGFR and HbA1c, if both local and Central Lab results are available for a given date then the Central lab value will be used.

For medication use, baseline use is defined as recorded data for which the start date of the medication is on or before treatment start date and the end date is on or after the treatment start date or ongoing or missing.

For subjects not receiving any study treatment, who therefore have no study treatment start date, baseline values and baseline medication use will be determined based on date of randomization.

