11.13. Appendix 13: Medication Groupings

11.13.1. Medication Groupings

Grouping
Non-insulin (NI) Population: Subjects having no baseline use of "Insulin"
Basal Insulin (BI) Population: Subjects having baseline use of "Basal insulin" but not "Prandial insulin" or "Mixed insulin"
Anti-hyperglycaemic agents (composed of the following):
Insulin
Basal insulin
Prandial insulin
Mixed insulin
Biguanide
Metformin
Sulfonylurea
Non-sulfonylurea secretagogue
Thiazolidinedione
Alpha-glucosidase inhibitors
DPP-IV inhibitors
SGLT-2 inhibitor
GLP-1 analogues other than study drug
Other anti-hyperglycaemic agent.

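### Insulin started during the trial is recoded as baseline use if its start date is blank, or partial in the month or year of first dose, so the subject leaves NI or BI instead of counting as an event

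*SAP*

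**What the plan says.** Four parts of the SAP act together.

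- **Imputation (11.7.2.2, Medications).** For partial dates: "Partial start dates of medications will be imputed as the earliest possible date consistent with the partial date". For a completely missing date: "the start date will be assumed to be prior to date of the first administration of study drug".
- **Baseline use (11.5.2.1).** The start condition is that "the start date of the medication is on or before treatment start date". The end condition is that "the end date is on or after the treatment start date or ongoing or missing".
- **Populations (4 and 11.13.1).** NI is defined by "Subjects having no baseline use of" insulin. BI requires baseline basal insulin without prandial or mixed insulin. On the data source, section 4 says "Subjects will be included in the NI population based on medication data recorded in the eCRF", with a matching statement for BI. Neither section makes an exception for imputed dates.
- **Endpoint (11.6.4, Metabolic Management Events).** "Initiation date is the date of the earliest medication use after treatment start date". This section has its own rule for a missing stop date but none for a missing start date, so nothing there overrides 11.7.2.2.

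Other rules in 11.7.2.2 do set bounds. Imputed death and CV event dates cannot fall before randomization, microvascular events are treated like CV events, and partial AE start dates must agree with the assigned treatment state.

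**The concern.** NI and BI should be fixed by what was true at baseline. Under these rules, membership can depend on how the endpoint event itself was recorded after randomization. A subject not on insulin at first dose who starts it later with no recorded date is classed as a baseline user and removed, so both the event and the subject disappear from the time-to-insulin analysis. Among subjects truly off insulin at baseline, only initiators can be lost this way.

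If the undated insulin is basal only, the subject is also placed in BI as if on basal insulin from the start. A BI subject who starts prandial or mixed insulin with a blank date is likewise dropped from BI.

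The same baseline flag feeds the baseline-insulin subgroup of MACE (11.10.1), the sulfonylurea/insulin strata for severe hypoglycaemia and the insulin strata for malignant neoplasms (8.2.1, 8.2.2).

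**Working it through.** The plan gives no figure on this point. Its 611-event target reproduces: 4 × (1.960 + 1.282)² / (ln 1.3)² = 610.6, rounded up to 611. It does not depend on medication dates.

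**Step 1: the end condition.** Insulin started after first dose has an end date after treatment start, or is ongoing, or has no end date. It therefore always meets the end condition, and only the imputed start date decides baseline status.

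**Step 2: apply the rules.** Take treatment start as 15 Mar 2016 (illustrative) and count study-treatment days from 1.

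| True insulin start | Day missing | Month and day missing | Blank |
|---|---|---|---|
| 25 Mar 2016 (day 11) | 01 Mar 2016: baseline | 01 Jan 2016: baseline | baseline |
| 20 Apr 2016 (day 37) | 01 Apr 2016: event, day 18 | 01 Jan 2016: baseline | baseline |
| 10 Oct 2016 (day 210) | 01 Oct 2016: event, day 201 | 01 Jan 2016: baseline | baseline |
| 10 Feb 2017 (day 333) | 01 Feb 2017: event, day 324 | 01 Jan 2017: event, day 293 | baseline |

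A blank date always becomes baseline use. A partial date does so only when the recorded month (day missing) or year (month and day missing) is that of treatment start. Otherwise the subject stays in NI with an event dated too early.

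**Step 3: share of incomplete dates recoded.** Assumptions, not from the SAP: treatment starts uniform over the calendar year, true insulin starts uniform over the next 548 days (18 months).

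- Blank: 100%.
- Year only: U uniform on 0–12 months, T uniform on 0–18; P(U + T < 12) = (12²/2) / (12 × 18) = 0.333. Counting days over 2016 also gives 0.333.
- Day missing: U uniform on 0–1 month; P(U + T < 1) = (1/2) / (1 × 18) = 0.028. Counting days gives 0.027.

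**Step 4: share of all initiations lost.** Let b, y and d be the proportions of initiations with blank, year-only and day-missing dates. Then loss ≈ b + 0.333y + 0.027d. A 2% loss needs b = 2%, or y = 0.02/0.333 = 6%, or d = 0.02/0.027 = 74%, each acting alone. A 5% loss needs b = 5% or y = 15%; day-missing dates alone cannot reach it. The SAP gives none of b, y or d.

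**Step 5: hazard ratio.** To a first approximation the hazard ratio is multiplied by (1 − loss, albiglutide) / (1 − loss, placebo). Proportionally equal loss leaves it unchanged. A purely hypothetical 5% against 2% gives 0.95/0.98 = 0.97; the reverse gives 0.98/0.95 = 1.03.

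**The case against.** The strongest points on the other side are these.

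- **Partial dates.** A reader might infer that every partial or missing start date is pushed before first dose. The SAP does not say that. The pre-dose assumption covers only completely missing dates, and a partial date from a later month or year stays after baseline. This stands.
- **Frequency.** Diabetes medication is scheduled for recording at baseline and about every 4 months (11.2), and cleaning precedes database freeze (3.2). An in-trial start known only by year is probably uncommon, and a blank date may more often belong to long-standing therapy, where the pre-dose assumption is right. This is plausible, but the SAP gives no count either way.
- **Bias between arms.** A reader might infer a biased hazard ratio. The trial is double-blind, and nothing in the SAP suggests that date recording differs by arm. Lost events are shown to be possible; a between-arm difference is not.
- **Convention.** One medication rule has to serve prior as well as in-trial therapy, so the contrast with AE and CV event dates is imperfect. That explains a general default, but not the lack of an exception where medication dates define an endpoint and its population.
- **Feasibility.** The visit schedule lists diabetes medication at each visit, but 11.6.4 takes insulin use from the Concomitant Medications form, and 6.2.3 describes by-visit recording only for cardiovascular medications. The SAP does not establish that a by-visit insulin record exists, so a repair cannot rest on one alone.

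None of this removes the misclassification of a blank in-trial start.

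**Conclusion.** The point holds in a limited form. As written, the rules recode an in-trial insulin start as baseline use when its date is blank, or when it is partial and names the month or year of treatment start. This is a stated rule with a wrong result, not a gap in detail.

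The recoded shares are 100% of blank dates by rule, and about 33% of year-only and 3% of day-missing dates under the uniform-timing assumptions. The number of events lost and any effect on the hazard ratio cannot be derived from the SAP.

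The reach is modest: two secondary endpoints reported with nominal p-values (11.11.1), a MACE subgroup interpreted only descriptively, and the insulin and sulfonylurea/insulin safety strata. A reader might infer that the primary result is at risk. It is not: that model is fitted in the ITT population with treatment as its only covariate (7.1.2). The point is worth correcting before unblinding because the repair is cheap.

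**What to change.** In 11.7.2.2, add an exception for anti-hyperglycaemic medications:

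1. Where eCRF data collected at or before baseline show that the agent was not in use, impute a blank or partial start date as the earliest date that agrees with the record and falls after treatment start (after randomization if never dosed).
2. Set NI and BI membership and the baseline-insulin flags from that same baseline information, not from imputed dates. Both steps are needed: the endpoint counts the earliest use after treatment start, so correcting membership alone would leave an imputed start lying before it.
3. Where the eCRF cannot place a record before or after first dose, keep the current rule and add a sensitivity analysis of both insulin endpoints that counts such records as in-trial starts.

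The cost is a few sentences, a small derivation change and one extra analysis, with no new data collection. One side effect should be acknowledged: a blank date would become the day after treatment start, which dates the event early and can lengthen the apparent duration of use judged against the 3-month requirement.
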